Study Rationale	
In the United States patients commonly undergo esophagogastroduodenoscopy (EGD) for upper abdominal symptoms to try to resolve whether they have gastroesophageal reflux disease or functional dyspepsia, if they are older than the age of 60 with symptoms, or have alarm symptoms such as unexplained weight loss, persistent nausea and vomiting or if they have symptoms that are refractory to acid suppression therapy. Given the increasing burden of digestive disease in the United States, the use of EGD is increasing in volume nationwide. EGD usually requires either conscious sedation or monitored anesthesia sedation, which has put an additional cost burden on the healthcare system. Since MCC or MCC-T does not require sedation, it offers an attractive option for both patients and clinicians alike.
 
The aim of this study is to compare in the same patient the accuracy of the MCC and MCC-T and EGD in patients presenting with upper abdominal symptoms.

Objectives	
Primary:
 
 1. To demonstrate the effectiveness of the MCC and MCC-T compared to EGD in identifying lesions in patients presenting with upper abdominal symptoms. 2. To evaluate rates of adverse events and overall safety of MCC and MCC-T as compared to EGD. 
Secondary:

	
 1. To compare rates of complete examination of the foregut by MCC and MCC-T and EGD in patients presenting with upper abdominal symptoms using sets of predetermined still images. 2. To assess patient satisfaction for patients undergoing MCC or MCC-T or EGD.
Study Design	Prospective, single center, tandem study.
Study Duration	
Total duration of the study for each patient will be 7-14 days including follow-up 24 hrs. after the final study related procedure.
 
Total anticipated study duration, including data analysis and final report, is estimated to be up to 12 months.

Study Endpoints	
Primary
 
Effectiveness:
 
For both MCC, MCC-T and EGD, rates of diagnosis of clinically relevant pathology in patients with upper abdominal pain will be assessed. Detection of D2 findings (clinically relevant) will be considered positive. Sensitivity, specificity, positive predictive value, and negative predictive values will be calculated for both MCC or MCC-T and EGD. In this study the “gold standard” will be the expert group’s decision regarding the presence of a relevant finding. McNemar’s test will be used to assess for statistically significant differences between the two modalities. Sub-analyses will be performed to compare accuracies of the two modalities based on anatomic region (i.e. esophagus, stomach, duodenum) and across various lesions (i.e. ulcers, gastropathy, esophagitis, etc.).
 
Safety: Rate of device or procedure related adverse events during the procedures or in the follow-up period (24 hrs. post procedure).
 
Secondary
 
Examination completion: Compare rates of complete examination of the foregut by MCC, MCC-T and EGD in patients presenting with upper abdominal complaints using sets of predetermined still images
 
Patient Satisfaction: Assess patient satisfaction for patients undergoing MCC or MCC-T and EGD.

Inclusion Criteria	
 1. Patient is 18 years up to 75 years 2. Patient is able to provide informed consent

	
 3. Patient has appropriate indications for EGD including symptoms of, but not limited to upper abdominal pain, acid reflux, heartburn, iron deficiency anemia, weight loss, bloating, belching, nausea, vomiting and atypical chest pain. 4. Patients are COVID-19 negative by PCR testing 1-3 days prior to EGD or fully vaccinated against SARS-CoV-2 (at least two weeks after final dose of authorized or approved vaccine) and completion of a symptom screening questionnaire before participating in the study.
Exclusion Criteria	
 1. Patient with dysphagia. 2. Patient with previous intestinal surgery. 3. Patient with Crohn's disease or other potential obstructive conditions, unless there is a recent CTE, MRE or patency capsule performed to exclude an obstructive lesion that may retain the capsule. 4. Female patient who is pregnant. 5. Patient with implanted medical device that would be potentially affected by magnets or radiofrequency emissions (e.g., pacemakers, implanted cardiac defibrillators). 6. COVID-19+ or with symptoms consistent with the infection. Fever, new cough, myalgias, and chills
Study Population and Sample Size	Since there is no predicate data in the USA, we plan a pilot study with 100 patients and 10 volunteers to help optimize the use of the MCC and MCC-T

1 RATIONALE FOR CONDUCTING THE INVESTIGATION

Since its introduction in 2001, video capsule endoscopy (VCE) has developed an increasing role in the management of luminal gastrointestinal disease. New guidelines supported by the American College of Gastroenterology and the American Society of Gastrointestinal Endoscopy recommend that VCE be considered the gold standard test for the assessment of most small bowel diseases. Capsules have also been developed to image the esophagus, stomach, and colon and to measure intestinal physiological parameters. Despite these advances, most of these new capsules are still passive devices, meaning that they travel through the gastrointestinal tract propelled by peristalsis. While this

has been successful for the evaluation of the small bowel, detailed examinations of the stomach and proximal duodenum require active control of the device for optimal imaging.

NaviCam is a new magnetically controlled capsule (MCC or MCC-T) that clinicians can control and more closely examine the foregut. The magnetically controlled capsule comes in two versions, either as a free-floating device or with a tether that can retard its progress down the esophagus. It then can be released from the tether to become the free-floating device for examining the stomach and duodenum. The former version has been subject to evaluation and to studies in China, these are detailed in the summary of clinical experience. Unpublished data on 25 patients with tethered device is also described below.

In the United States patients commonly undergo esophagogastroduodenoscopy (EGD) for upper abdominal symptoms to try to resolve whether they have gastroesophageal reflux disease or functional dyspepsia, if they are older than the age of 60 with symptoms, or have alarm symptoms such as unexplained weight loss, persistent nausea and vomiting or if they have symptoms that are refractory to acid suppression therapy. The burden of digestive disease in the United States, is increasing nationwide with a parallel increase in the use of EGD. Given that conventional EGD usually requires either conscious sedation or monitored anesthesia sedation, this has put an additional cost burden on the healthcare system. Since MCC does not require sedation, it offers an attractive option for both patients and clinicians alike.

Early iterations of the MCC were not ideal for examining the esophagus, due to relatively low frame rates. However, the latest version has a tether that allows for maneuvering the device within the esophagus. The tether can then be removed after the MCC has entered the stomach and the MCC can be manipulated by the magnetic field. Alternatively, by moving the magnet to the thorax it has been shown in volunteers that it is possible to slow the magnet down as it traverses the esophagus

The aim of this study is to compare in the same patient the accuracy of the MCC and MCC-T and EGD in US patients presenting with upper abdominal symptoms

2 SUMMARY OF CLINICAL EXPERIENCE

ANKON Medical Technologies, the Chinese company sister of AnX Robotica, sold about 300,000 NaviCam Capsules between 2016 to 2018. Additionally, the NaviCam Controllable System had been the subject of several articles published in scientific journals summarizing the results of clinical studies as well as real-life experience.

The Chinese FDA study was conducted to evaluate the clinical effectiveness of the NaviCam Stomach Capsule (MCC). The primary objective of the study was to compare NaviCam Stomach Capsule procedure with EGD in subjects diagnosed with gastro duodenal lesions.

The study was conducted in two centers in China all patients underwent the NaviCam Stomach Capsule procedure, followed by conventional EGD without sedation. The sensitivity, specificity, positive predictive value, and negative predictive value of detection of gastric focal lesions by MCC

were calculated, using EGD as the gold standard. One hundred subjects were enrolled in the study, but one subject refused to undergo EGD, therefore the statistical analysis was done on 99 subjects.

No adverse events were reported for any of the patients in this study. With respect to performance, the NaviCam Stomach Capsule was found to be equivalent to the EGD gold standard. All capsules were successfully expelled rectally with an average passage time of 76.1 hours.

The primary objective of the second comparative study was to compare a procedure with the MCC with gastroscopy for subjects diagnosed with gastric focal lesions. The study was conducted in 7 centers in China in which all patients underwent an MCC procedure followed by conventional gastroscopy 2 hours later without sedation. The sensitivity, specificity, positive predictive value, and negative predictive value of detection of gastric focal lesions by the MCC were calculated, using gastroscopy as the gold standard. A total of 353 subjects were enrolled in the study, but three subjects refused to undergo gastroscopy, therefore the statistical analysis was done on 350 subjects.

With respect to performance, the MCC was found to be equivalent to conventional gastroscopy in visualizing gastric mucosa. A total of 9 adverse events were reported in 5 (1.4%) of the 350 patients who completed this study. Three patients had abdominal distension and nausea, 1 patient had headache and vomiting, and 1 patient had foreign body sensations. In 4 of these 5 patients, adverse events including abdominal distension, nausea, vomiting, and headache were considered to be related to gastric preparation. All reported symptoms were resolved within 24 hours after ingestion of the capsule. Moreover, because of the noninvasiveness of the MCC procedure, more than 95% of patients preferred the MCC procedure as an initial diagnostic method.

Out of a total of 449 patients, only 5 patients reported mild adverse events which were all resolved within 24 hours. These results indicate that the MCC is safe, and any risks associated with the device and procedure are negligible when compared to the benefits of a minimally invasive procedure.

Additionally, a study utilizing the tether device was conducted in Changhai Hospital on 4 healthy volunteers and 21 patients with suspected esophageal disease. The MCC-T using the tether device was successfully carried out in all 25 participants. No adverse events were observed. Mean overall discomfort score during the procedure was 0.96 (range 0 – 3). NaviCam System diagnoses were in accordance with EGD in all 25 participants. The per-patient sensitivity of the NaviCam for esophageal disease detection was 100 %. The accuracy of the NaviCam for grading esophageal varices and reflux esophagitis were 66.7% and 100 %, respectively. (Unpublished). Additional unpublished data in volunteers has demonstrated that by moving the magnet over the chest with the patient in the prone position the MCC can be slowed down while it transits the esophagus.

On May 22, 2020 the company obtained FDA approval for the MCC device.

3 INVESTIGATIONAL PRODUCT

The NaviCam Capsule Endoscope System with NaviCam Stomach Capsule MCC-T, presented in Figure 1, is a novel endoscopic capsule imaging system intended to obtain images of the stomach. It differs from passive capsule endoscopy systems in that it uses magnetic fields to allow the position of the capsule to be controlled by an operator.

Figure 1: NaviCam Stomach System

The MCC-T includes the following key components:

1. Ingestible capsule for obtaining images
2. Data recorder for logging image data
3. Controller that allows the position of the capsule to be moved in 3D space.
4. Locator for determining the position of the capsule.
5. Tether device which connects to an ingestible capsule and allows for the visualization of the esophagus.

3.1 Capsule

The MCC (Figure 2) is an ingestible imaging device having an outer diameter of 12mm and a total length of 28mm.

The capsule captures images via a CMOS sensor. A clear top cover contains a compact objective lens in front of the CMOS. LEDs and a photoresistor are allocated around the objective lens. It consists of RF transmitter and an antenna for radio transmission. The capsule is powered by two silver oxide batteries.

Figure 2: NaviCam Stomach Capsule

The exterior of the capsule is designed with biocompatible polymer composites, polycarbonate and ethyl cyanoacrylate, which provide adequate tolerance to exposure to digestive juices and external compression. The capsule captures images at a frame rate ranging from 0.5 to 2 fps with a maximum resolution of 480x480 pixels.

3.2 Data Recorder

The NaviCam Data Recorder (Figure 3) is a portable data receiving unit powered by a built-in rechargeable lithium battery, which is placed inside an examination vest (Figure 4) worn by patient during examination. It is used to receive image data wirelessly transmitted from the capsule. The Data Recorder is charged with an included charger when not in use.

[figure not shown]

Figure 3: NaviCam Data Recorder

Figure 4: NaviCam Data Recorder in Examination Vest

3.3 Controller

The NaviCam Controller (Figure 5) is comprised of the following core components:

- Console
- Translational rotation platform
- Magnetic ball
- Examination bed

Figure 5: NaviCam Controller

During examination, the patient lies on the examination bed. The translational rotation platform with 5 degrees of freedom adjusts the movement of the magnetic ball to generate a corresponding magnetic field, and thereby to control the movement of capsule inside the patient's body.

The console is composed of a computer workstation installed with ESNavi Software, a monitor and joysticks to manually control the movement of translational rotation platform.

3.4 Locator

The NaviCam Locator (Figure 7) is a portable magnetic scanning device powered by a built-in rechargeable lithium battery. It is used to detect whether the capsule is inside the human body and probe its approximate position. This device negates the need for X-ray imaging.

Figure 7: NaviCam Locator

3.5 Tether

The Capsule Tether is an optional component which allows the visualization of the esophagus. The component is comprised of soft tubing which on one end is attached to a capsule cradle (to hold the capsule in place) and on the other end attaches to a 20ml standard syringe injection of water by the syringe detaches the capsule from the tether. (Figure 8).

[figure not shown]

Figure 8: Capsule Tether

4 STUDY OBJECTIVES

4.1 Study Objectives

Primary:

1. To demonstrate the effectiveness of the MCC and MCC-T when compared to EGD in identifying esophageal, gastric and duodenal abnormalities in patients presenting with upper abdominal symptoms.
2. To evaluate rates of adverse events and overall safety of MCC-T as compared to EGD.

Secondary:

1. To compare rates of complete examination of the foregut by MCC, MCC-T and EGD in patients presenting with upper abdominal complaints using sets of predetermined still images
2. To assess patient satisfaction for patients undergoing MCC, MCC-T and EGD.

4.2 Study Endpoints

Primary

Effectiveness:

For both MCC, MCC-T and EGD, rates of diagnosis of clinically relevant pathology in patients with upper abdominal pain will be assessed. Detection of D2 findings will be considered positive. Sensitivity, specificity, positive predictive value, and negative predictive values will be calculated for both MCC and EGD. In this study the “gold standard” will be the expert group’s decision regarding the presence of an abnormal finding. McNemar’s test will be used to assess for statistically significant differences between the two modalities. Sub-analyses will be performed to compare accuracies of the two modalities based on anatomic region (i.e. esophagus, stomach, duodenum) and across various lesions (i.e. ulcers, gastropathy, esophagitis, etc.).

Safety: Rate of device or procedure related adverse events during the procedures or in the follow-up period (24 hrs. post procedure).

Secondary

Examination completion: Compare rates of complete examination of the foregut by MCC or MCC-T and EGD in patients presenting with upper abdominal complaints using sets of predetermined still images

Patient Satisfaction: Assess patient satisfaction for patients undergoing MCC or MCC-T and EGD.

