10.2 Study Populations

The safety population will include all subjects who swallowed the NaviCam Capsule with tether and underwent upper endoscopy. All safety and efficacy analyses will be performed on the safety population.

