10.5 Efficacy Analysis

1) Clinical success – Diagnostic yield

For both MCC-T and EGD, we will be assessing rates of diagnosis of clinically relevant pathology in patients with upper abdominal pain. Detection of D2 findings will be considered positive. Sensitivity, specificity, positive predictive value, and negative predictive values will be calculated for both MCC-T and EGD. In this study the “gold standard” will be the expert group’s decision regarding the presence of a relevant finding. McNemar’s test will be used to assess for statistically significant differences between the two modalities. Sub-analyses will be performed to compare accuracies of the two modalities based on anatomic region (i.e. esophagus, stomach, duodenum) and across various lesions (i.e. ulcers, gastropathy, esophagitis, etc.).

2) Secondary Outcomes

Technical success:

- i. We will assess the ability of the -MCC-T and the EGD to photo document the esophagus, stomach, and duodenum as described in this protocol.
- ii. We will assess the ability of the MCC-T to be released upon command in the stomach once esophageal examination is complete.

Learning curves:

When training staff to use the device, we will assess how many capsules it takes to obtain “competency.” This will be defined as being able to obtain the appropriate photo documentation as described above at a 90% success level.

Patient satisfaction

Patient responses will be analyzed on a Likert scale to determine which procedure did the patients prefer.

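### The one McNemar test compares EGD with a capsule group that changes from section to section; taken literally, 10.2 and 10.5 leave a randomised arm out of the primary analysis

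*Combined protocol and SAP*

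**What the plan says.** The same primary effectiveness analysis is described in three places, each ending in one McNemar test between two modalities.

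- **Synopsis, Study Endpoints.** The four accuracy "values will be calculated for both MCC or MCC-T and EGD", which reads as the two capsule versions taken together.
- **4.2 Study Endpoints.** It opens with three devices: "For both MCC, MCC-T and EGD, rates of diagnosis of clinically relevant pathology in patients with upper abdominal pain will be assessed". It continues: "Sensitivity, specificity, positive predictive value, and negative predictive values will be calculated for both MCC and EGD". The test then "will be used to assess for statistically significant differences between the two modalities".
- **10.5 Efficacy Analysis**, under a diagnostic-yield heading: "For both MCC-T and EGD, we will be assessing rates of diagnosis of clinically relevant pathology". The untethered capsule is not mentioned.

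Three other sections bear on the test. Section 10.2 defines the population for all safety and efficacy analyses as "all subjects who swallowed the NaviCam Capsule with tether and underwent upper endoscopy". Section 10.6 allocates patients at random to MCC or MCC-T. Section 10.1 calculates the accuracy measures against EGD, whereas the synopsis, 4.2 and 10.5 use the expert group's decision. No section gives an alpha, says whether the arms are pooled, or names the measure that McNemar tests.

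**The concern.** Objective 1 in 4.1 is to demonstrate effectiveness against EGD for both capsule versions, and the only planned inference is this test. Three capsule groups are possible (MCC, MCC-T, both), and the sections do not agree on one. Following 10.2 and 10.5 as written would remove patients randomised to MCC from the primary analysis; following the synopsis would keep them. With the choice open, it can be made after the data are seen, and a literal reading discards about half of a small sample if allocation is equal. The conflict over the reference standard adds a second choice, because it decides whether a lesion found only by the capsule counts for or against the capsule.

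**Working it through.** The plan has no calculation to reproduce: 10.6 justifies the size only as a pilot without US predicate data.

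**Inputs.** From the documents: 70 patients (10.6), randomised to MCC or MCC-T (10.6), each with one capsule examination and one EGD. Assumed, because not stated: 1:1 allocation (35/35), two-sided 5%, the exact form of McNemar's test, and the discordance rates below. The synopsis gives 100 patients instead, so that size is shown too.

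**Formula.** With b patients positive on EGD only and c on the capsule only, d = b + c and exact two-sided p = 2 × P(X ≤ min(b, c)), X ~ Binomial(d, ½), capped at 1.

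**Step 1: does the grouping change the result?** (b v c)

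| Example | One arm | Other arm | Pooled |
|---|---|---|---|
| A | 6 v 0: 2/64 = 0.031 | 1 v 3: 2×(1+4)/16 = 0.63 | 7 v 3: 2×(1+10+45+120)/1024 = 0.34 |
| B | 4 v 0: 2/16 = 0.125 | 4 v 0: 0.125 | 8 v 0: 2/256 = 0.008 |

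In A, one arm is significant and the pooled test is not. In B it is the reverse.

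**Step 2: what does the choice cost in power?** Power = Σ over d of Binomial(d; n, p₁+p₂) × P(p ≤ 0.05 | d), where p₁ is the EGD-only rate and p₂ the capsule-only rate. At 15% v 5%:

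| | One arm | Pooled |
|---|---|---|
| 70 patients | 14% (n=35) | 37% |
| 100 patients | 24% (n=50) | 54% |

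At n=70 and 20% v 5% the figures are 30% and 67%; at 10% v 5% they are 3% and 11%.

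**Step 3: how often do the three groupings disagree?** In 40,000 simulated trials of 35/35 with 15% v 5% in both arms, at least one but not all three tests were significant in 39%. At 20% v 5% it was 61%.

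**Step 4: false positives.** With 10% v 10% in both arms, any of the three exact tests was significant in 4.9% of trials, because the exact test is conservative at this size. The plan does not name the version; with the uncorrected chi-square form the figure is 10 to 11%.

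**Step 5: measure and reference standard.** Under 6.7 the panel grades findings seen on either examination. If a panel D2 finding is both the test positive and the reference, every discordant patient is reference-positive, so diagnosis rate and sensitivity have the same b and c. With EGD as reference (10.1) they separate. Take 70 patients: 14 positive on both, 2 on EGD only, 10 on the capsule only.

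- Diagnosis rate: capsule 24/70 = 34%, EGD 16/70 = 23%; 2 v 10 gives p = 2×(1+12+66)/4096 = 0.039, in favour of the capsule.
- EGD as reference: the 10 capsule-only findings become false positives. Capsule specificity is 44/54 = 81% and PPV 14/24 = 58%. EGD scores 100% by definition, and McNemar on sensitivity is 2 v 0, p = 0.5.

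**The case against.** Four objections deserve an answer.

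- **It is a pilot.** True, and it makes a formal testing hierarchy unnecessary. But the plan itself schedules a significance test under an objective to demonstrate effectiveness, so it must say what is compared.
- **10.5 settles the matter.** Its heading suggests diagnostic yield, it names MCC-T, and 10.2 agrees with it. That is the most favourable reading, and the accuracy measures can then be taken as descriptive. It still contradicts the synopsis, 4.2 and objective 1 in 4.1, and leaves the randomised MCC arm without a place in the primary analysis.
- **Under the panel reference the measures coincide.** Step 5 agrees. The conflict over the group remains, and 10.1 leaves the reference itself unsettled.
- **The error rate is not inflated much.** Also accepted: step 4 shows about 5% with the exact test.

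A reader might infer more: that every listed measure crossed with every grouping is a separate primary test with a large family-wise error, or that capsule false positives could offset missed lesions and hide a worse capsule behind an equal yield. The documents do not support this. Overall accuracy appears only among sub-analyses, and no section applies McNemar to PPV or NPV. The procedure in 6.7 gives no route to a capsule false positive against the panel, and with EGD as reference EGD cannot err.

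**Conclusion.** The point holds as a contradiction between sections about which capsule group is tested, with an unnamed measure and conflicting reference standards alongside it. Its size is a power of about 37% against 14%, and disagreement between groupings in about 40% of trials, both at 15% v 5% discordance with an assumed 35/35 split, two-sided 5% and exact test. The examples in step 1 are possible data, not predictions. It would go too far to say that the groupings in those examples support opposite conclusions: they set a significant result against a non-significant one, not significance in both directions. The damage is to interpretation and precision. It should be corrected before analysis, but it does not invalidate the paired design.

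**What to change.** In the synopsis, 4.2 and 10.5, name one primary contrast: per-patient detection of panel-confirmed D2 findings, both randomised capsule arms pooled versus EGD, by exact McNemar at two-sided 5%, with the paired difference and its 95% CI. Pooling is valid because each patient contributes one capsule examination and one EGD.

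Amend 10.2 to include all patients who swallowed either capsule and had EGD. Make 10.1 use the same expert-panel reference as 4.2 and 10.5. Report sensitivity, specificity, PPV and NPV, and MCC versus EGD and MCC-T versus EGD separately, as descriptive estimates with 95% CIs. State that a non-significant McNemar result does not show equivalence, which matters given the power in step 2.

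This changes wording only and needs no new data. The sponsor gives up choosing the capsule version or the measure after seeing the results. The pooled estimate averages over two versions that may differ, which is why the separate estimates should stand beside it.
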